### **Study Therapy Control Group**

The current guidelines of the European Society of Cardiology do not recommend the use of ACE-inhibitors or ARB in the early stabilization of patients with acute HF (41). (37). The administration of previously prescribed ACE-inhibitors or ARB should be continued on admission with AHF, except in the presence of hemodynamic instability, hyperkalemia or severely impaired renal function. In these cases, the daily dosage of oral therapy may be reduced or stopped temporarily until the patient is stabilized. In the absence of a prescription, an initiation of the medication before discharge from hospital and up-titration every two to four weeks is recommended (37). Accordingly, patients in the control group will receive (1,2) oxygen application, treatment with diuretics based on extent of fluid overload and recent weight gain. The dosage thereby will be adjusted to renal function. Further on, after 24 to 48 hours, treatment with an ACE-inhibitor (or ARB) will be started in low dosages displayed in Figure 5b. After six to eight days of treatment, dosage of the ACE-inhibitor / ARB will be up-

titrated following the schedule displayed in Figure 5b dependent on hemodynamic and renal tolerance. As in the Intervention group, in patients with chronic HF and a LVEF below 35%, the treating physician may at any time (both in-hospital and after hospitalization) consider to replace a preexisting therapy with an ACE-inhibitor or ARB with LCZ696 as recommended in the 2016 ESC guidelines (36). Should the patient already be on LCZ696 (“Entresto”), the dosage will remain unchanged for the first 4 to 5 days with the option of increasing the dose by 25% at the end of hospitalization (if not already at 200 mg b.i.d).

Transdermal nitrates can be used, but only in the doses currently approved in Switzerland (e. g. Nitroderm TTS 5 mg / 12 h or 10 mg / 12h). The use of nitrates or hydralazine in higher doses is strongly discouraged. The use of a specific blood pressure target is up to the discretion of the treating physician.

Should the patient be already treated with another ACE-inhibitor / ARB not listed in the therapy schedule (Figure 5b), again the previously prescribed ACE-inhibitor / ARB will be continued in an unchanged dosage if tolerated for the first two to three days after which up-titration will then be performed in a comparable way like demonstrate for the ACE-inhibitors / ARBs listed in Figure 5b. Accordingly up-titration of 50% will be performed every seven to 21 days to the maximum tolerated dose in order to achieve adequate inhibition of the renin–angiotensin–aldosterone system (37).

Control group	Starting dose (mg)	Target dose (mg) * if patient is still hospitalised
transdermal Glyceryl trinitrate (i.e. Nitroderm® TTS) [mg / 12 h]	0 - 10	0 - 10
Ramipril (i. e. Triatec®) [mg/d] 	2.5 o.d.	10 o.d.
Lisinopril (i. e. Zestril®) [mg/d] 	2.5–5.0 o.d	20–35 o.d.
Enalapril (i. e. Reniten®) [mg/d] 	2.5 b.i.d.	20 b.i.d.
Captopril (i. e. Capoten®) [mg/d] 	6.25 t.i.d.	50 t.i.d.
Candesartan (i. e. Atacand®) [mg/d] 	4–8 o.d	32 o.d
Losartan (i. e. Cozaar®) [mg/d] 	50 o.d.	150 o.d.

 Only one ACE-inhibitor should be started.  
 ARB will only be initiated if ACE-inhibitor intolerance is known.

**Figure 5b:** Treatment algorithm for the control group as recommended by the current ESC guidelines.

### Duration of Treatment with Study-Specific Medication

The study-specific medication with hydralazine in the goal-directed therapy group ends after 48 h after enrolment in the study. The dosage of glycerol trinitrate and up-titration with ACE-Inhibitors and / or ARBs in both groups will be performed according to the treatment algorithms in Figures 5a and 5b during the hospital stay until discharge. Information about discharge medication will be given for both groups; if necessary the discharge summary will provide instructions for maintenance dosage or further up-titration of ACE-inhibitors and / or ARBs to the treating physician in ambulant setting.

### Patient Safety: Symptomatic Arterial Hypotension

If systolic blood pressure should fall below the target of 90 mm Hg to 110 mm Hg and signs or symptoms of arterial hypotension occur, an adjustment of medical therapy following a predefined schedule will be performed:

- **Day 1 and 2 (0 h till 48 h):** Reduction of 50% of the transdermal applied nitrates by immediate removal of the patches and temporary withdrawal of hydralazine. Additionally blood pressure monitoring will be performed every 30 minutes to 60 minutes until hemodynamic stability has been reestablished.
- **Day 3 till discharge:** Reduction of 50% of the transdermal applied nitrates by immediate removal of the patches and temporary dosage reduction of the ACE-inhibitor or ARB to the dosage of the last day when the patient was asymptomatic. Additionally blood pressure monitoring may be performed if deemed necessary.
- **At any time during the study:** If these measures do not help to increase systolic arterial blood pressure, physical measures like the elevation of the patient's legs and as an ultima ratio intravenous administration of crystalloid fluid can remove symptoms and hemodynamic impairment. After termination of the symptomatic hypotensive episode, a stepwise augmentation of transdermal nitrates, hydralazine or ACE-inhibitor / ARB will be reinitiated.

Importantly, asymptomatic hypotension without evidence for critical organ dysfunction will not lead to any change in medical therapy, as maximal afterload reduction is an integral part of the intervention.

### **Patient Safety: Worsening Renal Function**

Some rise in creatinine and blood urea nitrogen levels is commonly seen in patients with acute HF. Often it is not possible to identify a single cause, but hypovolemia induced by diuretic treatment, low output as part of acute HF, renal venous congestion or initiation of ACE-inhibitors / ARB may play a role. Regarding the up-titration of ACE-inhibitors / ARB current guidelines suggest that changes in creatinine or blood urea nitrogen levels should not be considered clinically important unless they are rapid and substantial (41). Accordingly, a creatinine rise less than 50% from baseline values will be carefully monitored without adjustment of treatment schedule. In case of a rise of more than 50% of the baseline value, the treatment with ACE-inhibitors / ARB will be continued without augmentation and creatinine levels will be monitored every 24 hours to 48 hours. As soon as creatinine levels begin to decline, dosage of ACE-inhibitor / ARB will be up-titrated according to the treatment schedule (Figures 4a / 4b). In case of acute renal injury, defined as a doubling in serum creatinine levels compared to baseline levels (42), the following procedural schedule will be applied: A 50% reduction of the last ACE-inhibitor / ARB dosage will be performed and creatinine levels will be measured 24 hours to 48 hours later. When creatinine levels continue to rise despite this measure, a further stepwise decrease of 50% of the ACE-inhibitor / ARB is scheduled and will be repeated every 48 hours until creatinine levels begin to decline. When creatinine levels remain unchanged or decrease less than 30% of peak level, the current dosage of ACE-inhibitor / ARB will remain unchanged. As soon as creatinine levels decrease at least 30% to peak value, the initial study therapy schedule will be continued (Figures 4a / 4b). As the

dose of diuretics is an important contributor to renal injury, diuretic dose will also be reduced by at least 50% in patients with renal injury.

If systolic blood pressure still persists over 140 mm Hg despite the treatment schedule described above during day 3 to 6, higher doses of ACE-inhibitors or ARBs are recommended. The addition of a calcium-channel blocker (preferably amlodipine, Norvasc®(43) can be considered alternatively. The use of beta-blockers and spironolactone will be identical to that described in the control group.

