On day 2 (24 h till 48h) the dosage of transdermal nitrates will be adjusted according to systolic blood pressure. In addition, at 24 hours after study inclusion, therapy with a peroral ACE-inhibitor or in case of ACE-inhibitor intolerance an ARB will be initiated. Should the patient be already on an ACE-inhibitor, the dosage remains unchanged for the first 24 hours. On day 2 (after 24 hours) the ACE-inhibitor will be up-titrated according to therapy schedule (Figure 5a) starting from day 2. Thereby, the up-titration will be performed on the top of the precedent ACE-inhibitor / ARB dosage. Should the patient be already on a maximal dosage of an ACE-inhibitor, an ARB will be added at low dose once daily and up-titrated according to the therapy schedule. In patients with chronic HF and a LVEF below 35%, the treating physician may at any time (both in-hospital and after hospitalization) consider to replace a preexisting therapy with an ACE-inhibitor or ARB with LCZ696 as recommended in the 2016 ESC guidelines (37). Should the patient already be on LCZ696 (“Entresto”), the dosage remains unchanged for the first 24 hours. On day 2 (after 24 h) the dose of LCZ696 will be up-titrated by 25% if not already on target dose (200 mg b.i.d.). Again, the dose should be increased by 25% at the end of hospitalization (if not already at 200 mg b.i.d.).

Intervention group	day 1 at hospital admission		day 1 6 h after admission		
	< 130 	> 130 	90 - 110	111 - 130	> 130
systolic blood pressure [mm Hg]	< 130 	> 130 	90 - 110	111 - 130	> 130
per oral Glyceryl trinitrate capsule (i.e. Nitroglycerin Streuli ® ) 0.8 mg  or Spray (i.e. Corangin Nitrospray ® ) 0.4mg	3 or 6 applic.	3 or 6 applic.			
transdermal Glyceryl trinitrate (i.e. Nitroderm ® TTS) [mg / 24 h]	40 - 60	60 - 80	+ 0	+ 20 - 40	+ 20 - 60
Hydralazine (i. e. Hydrapres ® ) 25 mg	1 - 1 - 1 - 1	1 - 1 - 1 - 1	1 - 1 - 1 - 1	1 - 1 - 1 - 1	1 - 1 - 1 - 1
Ramipril (i. e. Triatec ® ) [mg/d] 					
Lisinopril (i. e. Zestril ® ) [mg/d] 					
Enalapril (i. e. Reniten ® ) [mg/d] 					

-  The lowest blood pressure value measured at the emergency department before study inclusion will be considered.

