### Important Treatment Rules

- ACE-inhibitor can be administered once or twice per day. ARB should be administered only once a day.
- If Patient is already on ACE-inhibitor or ARB continue dosage unchanged during day 1 and perform up-titration following day 2 till 7 schedule.
- If the patient is already treated with another ACE-inhibitor / ARB than listed in the schedule, previously prescribed ACE-inhibitor / ARB should be continued unchanged during day 1. A daily up-titration of approximate 50% (25% to 75% depending on blood pressure response) starting from day 2 is recommended. The maximal dosage should be achieved at day 5 to 7 of treatment if well tolerated.
- If creatinine levels rise more than 50% from baseline continue ACE-inhibitor / ARB in unchanged dosage to creatinine levels begin to decline. Then continue up-titration according to the treatment schedule.
- If creatinine levels rise more than 100% from baseline reduce ACE-inhibitor / ARB treatment by 50% and continue therapy with unchanged dosage until creatinine levels decline more than 30%.
- Treatment with any diuretics or aldosterone-antagonists at any time is at discretion of treating physician and not determined by the study protocol.

**Figure 5a:** Treatment algorithm for the early goal-directed therapy group (continuation).

On day 3 a further up-titration of the ACE-inhibitor / ARB depends on systolic blood pressure according to Figure 5a will be performed. In patients on LCZ696, the dose of LCZ696 remains unchanged. The dosage of transdermal nitrates will be gradually decreased from day 3 till hospital discharge (Figure 5a). Also, intermittent dosing (12 hours nitrates, 12 hours nitrate-free period) will be used from day 3 on. Typically, we would use in half the dose applied at day 2 and apply the patches from 8:00 h am till 8:00 h pm.

On day 4 till day 7 a further up-titration of the ACE-inhibitor / ARB dependent on systolic blood pressure according to Figure 5a will be performed. In patients on LCZ696 the dose of LCZ696 will be up-titrated by again 25% if not already on target dose (200 mg twice daily).

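### Intervention patients whose creatinine has doubled and is still rising fall under two incompatible ACE-inhibitor/ARB rules, and under two incompatible diuretic rules

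*Combined protocol and SAP*

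**What the plan says.** Two places in protocol section 5 deal with a doubling of creatinine.

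- **Important Treatment Rules** (the box attached to Figure 5a, so the intervention arm). For a rise above 100% the instruction is to "reduce ACE-inhibitor / ARB treatment by 50% and continue therapy with unchanged dosage until creatinine levels decline more than 30" per cent. On diuretics the same box says: "Treatment with any diuretics or aldosterone-antagonists at any time is at discretion of treating physician and not determined by the study protocol".
- **Patient Safety: Worsening Renal Function.** At a doubling, the drug is halved and creatinine is measured again 24 to 48 hours later. If it is still going up: "When creatinine levels continue to rise despite this measure, a further stepwise decrease of 50% of the ACE-inhibitor / ARB is scheduled", repeated every 48 hours until it starts to come down. If it is flat or only slightly lower: "When creatinine levels remain unchanged or decrease less than 30% of peak level, the current dosage of ACE-inhibitor / ARB will remain unchanged". On diuretics: "diuretic dose will also be reduced by at least 50% in patients with renal injury".

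The General Procedure for Both Groups also leaves loop diuretics to the treating physician, as do the protocol Summary and the SAP synopsis (SAP section 1). Neither document ranks the rule box against the safety section.

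**The concern.** A physician who meets a doubled and still rising creatinine is told by the dosing algorithm to keep the halved dose, and by the safety section to halve it again. The same physician is told both that the protocol does not set the diuretic dose and that it must be cut by at least half.

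The protocol lists 17 sites. Two of them can each comply fully and still treat this patient differently. The stakes are patient safety and uniformity of the intervention. Section 6 treats reduced renal blood flow following hypotension as part of the main risk of the strategy, creatinine at 48 h and at discharge is a secondary endpoint, and a creatinine rise above 30% is a collected adverse event (SAP section 11).

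**Working it through.** There is no planned figure to reproduce. The check compares the two rules, then works out how far the doses diverge.

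**1. Where the rules differ.** The trigger is effectively the same (a rise above 100%, or a doubling), and so is the first step (halve). After the first cut, taking the rule box's 30% as a fall from peak, which the box does not state:

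| Creatinine at recheck | Rule box, Figure 5a | Worsening Renal Function | Compatible? |
|---|---|---|---|
| Still rising | Hold | Halve again, repeat every 48 h | No |
| Flat, or down by less than 30% | Hold | Hold | Yes |
| Down by exactly 30% | Hold | Resume schedule | Trivial difference |
| Down by more than 30% | Hold ends | Resume schedule | Yes |

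The ACE-inhibitor/ARB conflict is confined to the first row.

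**2. Size of the dose gap.** Let D be the dose at doubling, with creatinine still rising at each check.

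- Rule box: 0.5 × D throughout.
- Safety section: 0.5 × D, then 0.5² × D = 0.25 × D, then 0.5³ × D = 0.125 × D.
- Ratio: 0.5 / 0.25 = 2 after the second cut; 0.5 / 0.125 = 4 after the third.

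**3. Example in mg/day.** Figure 5a, day 3, systolic pressure 111–130 mm Hg. D is taken as the middle of the permitted range (an assumption made for illustration).

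| Drug | Range | D | Rule box | Safety section, 2nd cut | Safety section, 3rd cut |
|---|---|---|---|---|---|
| Enalapril | 5–10 | 7.5 | 3.75 | 1.88 | 0.94 |
| Lisinopril | 5–7.5 | 6.25 | 3.13 | 1.56 | 0.78 |
| Candesartan | 8–16 | 12 | 6 | 3 | 1.5 |

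**4. Timing.** Let the first cut be at hour T. Assume the second is made at the 24–48 h recheck and the third 48 h after that. The second then falls at T+24 to T+48 and the third at T+72 to T+96. Figure 5a ends at 168 h.

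| Injury on | T (h) | 2nd cut (h) | 3rd cut (h) |
|---|---|---|---|
| Day 3 | 48–72 | 72–120 | 120–168 |
| Day 4 | 72–96 | 96–144 | 144–192 |
| Day 5 | 96–120 | 120–168 | 168–216 |
| Day 6 | 120–144 | 144–192 | beyond the table |

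The 2-fold gap therefore opens within the Figure 5a schedule for any injury up to day 5, and in part for day 6. The 4-fold gap does so for injury by day 3, and in part for day 4.

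**5. Diuretics.** The box requires no change and says that the protocol does not set the dose. The safety section requires a cut of at least 50%. Both statements cannot hold for a patient with renal injury.

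**The case against.** The best reply is that the rule box is shorthand and the safety section is the full procedure. Trigger, first step and release point nearly match, and a clinician facing kidney injury would turn to the safety section, which adds only the still-rising branch. This fails on the wording: the box gives its own end condition, a fall of more than 30%, and that excludes a second cut. It does not refer the reader to the safety section.

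Section 7 (Study Withdrawal) also requires the drug concerned to be adjusted or stopped for events such as acute kidney injury. A site that cuts further therefore has authority to do so, and the harm is limited. But section 7 is satisfied by either rule and selects neither.

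On diuretics, the safety text can be read as a specific exception to a general discretion. That reading is reasonable, but the box says discretion applies at any time, with no carve-out.

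Several cautions stand. The rules are incompatible rather than opposed in direction, since neither raises the dose while creatinine is rising. The smallest doses in the example are arithmetic, not likely prescriptions. The 4-fold gap needs creatinine to keep rising over 72–96 h with no suspension. The 168 h limit is the end of the table, not of treatment, because titration continues until discharge. The diuretic conflict may reach the control arm too, since the General Procedure covers both groups.

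**Conclusion.** The concern holds. In the intervention arm, a patient whose creatinine has doubled and is still rising after the first cut is given two ACE-inhibitor/ARB instructions that cannot both be followed. The doses then differ 2-fold after one further cut and 4-fold after two. The diuretic instructions conflict for any patient with renal injury. These sizes rest on literal application of each rule and, for the timing, on the assumed spacing of cuts.

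The documents give no incidence of renal injury, so how many of the roughly 385 intervention patients would be affected cannot be stated. No power figure or primary analysis changes. It should be corrected because a safety rule has to give one answer.

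**What to change.** Replace the bullet in Important Treatment Rules on a rise above 100% with the safety section's rule: halve the dose; recheck creatinine at 24–48 h; if it is still rising, halve again and repeat every 48 h until it begins to fall; if it is flat or down by less than 30% from peak, hold; once it is down by at least 30% from peak, resume titration.

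For diuretics, choose one intention. If the mandatory cut is meant, add an exception for renal injury to the rule box, the General Procedure for Both Groups, the protocol Summary and the SAP synopsis. If discretion is meant, turn the safety section's sentence into a recommendation.

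Two clerical items, which carry no weight in the verdict, fit the same edit:

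- The safety section says of recovery only "As soon as creatinine levels decrease at least 30% to peak value, the initial study therapy schedule will be continued". State that titration resumes stepwise from the held or reduced dose, not from the column for that hospital day. This matches "the up-titration will be performed on the top of the precedent ACE-inhibitor / ARB dosage" for the intervention arm and "a stepwise augmentation of transdermal nitrates, hydralazine or ACE-inhibitor / ARB will be reinitiated" after hypotension.
- Its references to Figures 4a / 4b should be to Figures 5a / 5b.

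The cost is a few sentences in one amendment, with no added patients or visits and no blood tests beyond those the safety section already orders.

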## Summary

**Background:** In contrast to treatment for chronic heart failure, which is based on several large prospective randomized controlled trials, treatment for acute heart failure is largely based on uncontrolled studies, clinical experience and expert opinion. Perhaps at least in part related to the uncertainties in the treatment of acute heart failure, outcome of patients with acute heart failure is extremely poor. Mortality is 50% at three years. More than 85% of patients with acute heart failure are treated in the non-ICU / CCU setting - the Emergency Department and the regular medical ward. Unfortunately, appropriate treatment is particularly ill-defined in this setting.

**Aim:** to test the hypothesis that a comprehensive approach using an early goal-directed decrement of preload and afterload with a target systolic blood pressure of 90 to 110 mm Hg by aggressive vasodilatation in patients with acute heart failure in the non-ICU setting is safe, and leads to a better clinical and economical outcome.

**Methodology:** This is a prospective, randomized, controlled multicenter study designed to enroll 770 patients presenting with acute heart failure at the emergency departments at the participating study sites. Patients will be randomly assigned 1:1 after stratification for site and B-type natriuretic peptide (BNP, NT-proBNP) levels to an early goal-directed therapy or standard care according to current guidelines. Early goal-directed therapy applies aggressive vasodilatation using sublingual and transdermal nitrates, hydralazine to avoid tolerance to nitrates, and rapid up-titration of angiotensin converting enzyme inhibitors and angiotensin II receptor blockers with a target systolic blood pressure of 90mm Hg to 110 mm Hg. Timing and dosing of diuretics and all other treatments are left to the discretion of the treating physician in both groups. The primary endpoint is death or heart failure readmission within 180 days. Secondary endpoints include the quantitative assessment of dyspnea, need for admission to the intensive care unit, surrogate markers like BNP or NT-proBNP, the digitally recorded third heart sound, renal function, time to discharge, functional status and quality of life, falls, total treatment cost, and cost-effectiveness. Patients will receive extensive clinical and economic follow-up of at least 360 days. Endpoints will be adjudicated by a clinical endpoint committee blinded to group assignment.

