## 5. Procedures

Figure 4: Study procedures.

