### **General Procedure for Both Groups**

At any time in the study the use of further treatment including loop diuretics, aldosterone antagonists, morphine or other drugs or non-pharmacological therapies (including non-invasive ventilation) will always be dependent on the clinical conditions and will be at the discretion of the treating physician.

Non-invasive hemodynamic monitoring will be performed every 10 to 30 minutes during the first hour, every 30 to 90 minutes in the second to the fourth hour, and every 6 to 8 hours for the rest of the hospitalization as currently in practice at the enrolling institutions. Continuous recording of a three-channel ECG and transdermal oxygen saturation provided by automated monitoring systems will be applied as clinically indicated.

At the time of initial presentation and before discharge the patient leg circumference will be measured at three distinct points on either side: 10 cm distal from the caput fibulae, 5 cm above the ankles and at the middle of the metatarsi. The points of measurement will be marked. A special tape measure incorporating a spring exercising constant tension will be used ensuring a measurement independent of the strain applied by the investigator. Simultaneously and when possible, the central venous pressure will be obtained with a high resolution ultrasound imaging device combined with a translucent pressure manometer.

In addition, 15 ml of serum, EDTA plasma and urine will be collected at five time points (at baseline, at day 1, day 2, day 6 and discharge) for the measurement of biomarkers such as BNP, NT-proBNP, mid-regional pro-atrial natriuretic peptide, pro-adrenomedullin, copeptin, N-GAL, Cystatin C, Troponin T, and pro-endothelin that also reflect the response to treatment. The determination of NT-proBNP, mid-regional pro-atrial natriuretic peptide, pro-adrenomedullin, copeptin, N-GAL, Cystatin C, Troponin T, and pro-endothelin and pro-endothelin will be performed collectively after hospital discharge of patients and has no effect on patient treatment.

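### The Figure 5a treatment rules contradict the renal-safety schedule on ACE-inhibitor/ARB dose when creatinine has doubled and keeps rising, and on the diuretic cut in renal injury

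*Combined protocol and SAP*

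**What the plan says.** Two parts of protocol section 5 deal with a large creatinine rise.

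- **Important Treatment Rules (with Figure 5a).** Once creatinine is more than 100% above baseline, the instruction is: "reduce ACE-inhibitor / ARB treatment by 50% and continue therapy with unchanged dosage until creatinine levels decline more than 30" (per cent). A later bullet in the same list reads: "Treatment with any diuretics or aldosterone-antagonists at any time is at discretion of treating physician and not determined by the study protocol".
- **Patient Safety: Worsening Renal Function.** At a doubling of creatinine, the ACE-inhibitor or ARB is halved and creatinine is measured again 24 to 48 hours later. If creatinine is still going up, "a further stepwise decrease of 50% of the ACE-inhibitor / ARB is scheduled and will be repeated every 48 hours", until it starts to fall. If it is level, or less than 30% below its peak, the current dose stays. Once it is at least 30% below peak, the schedule resumes. The section adds that "diuretic dose will also be reduced by at least 50% in patients with renal injury".

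Two other places speak of diuretics in general terms. The Summary says: "Timing and dosing of diuretics and all other treatments are left to the discretion of the treating physician in both groups". General Procedure for Both Groups begins "At any time in the study the use of further treatment including loop diuretics" and goes on to make such treatment depend on the patient's clinical condition and the physician's judgement.

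The renal section also sends the reader to the wrong figures: "dosage of ACE-inhibitor / ARB will be up-titrated according to the treatment schedule (Figures 4a / 4b". The dosing algorithms are Figures 5a and 5b, and the only Figure 4 is captioned "Figure 4: Study procedures".

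**The concern.** The intervention is rapid up-titration on emergency and general wards at 17 listed sites. Duration of Treatment with Study-Specific Medication makes the Figure 5a and 5b algorithms operative until discharge, so the rules printed with Figure 5a are a natural bedside sheet. A patient whose kidney function is still worsening after the first dose cut is the one for whom the next step matters most, and that is where the two texts give different orders.

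With two written rules, a monitor cannot say consistently which conduct is a deviation. Creatinine at 48 hours and at discharge is a secondary endpoint, and a creatinine rise above 30% is a collected adverse event (SAP section 11). The affected treatment therefore bears on outcomes that the trial reports. The issue is patient safety and uniform delivery of the intervention; no statistical calculation depends on it.

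**Working it through.** The plan gives no figure to reproduce. The check sets the two rules side by side and follows the dose.

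**Trigger.** More than 100% above baseline (Important Treatment Rules) and a doubling (Worsening Renal Function) are the same clinical state. Both texts bind intervention-arm patients.

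**Branches after the first halving:**

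| Creatinine at recheck | Important Treatment Rules | Worsening Renal Function |
|---|---|---|
| Still rising | hold | halve again, repeat every 48 h |
| Level, or less than 30% below peak | hold | hold |
| Down by more than 30% | hold ends | resume schedule |

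The rules differ only in the first row. The Figure 5a bullet is not silent about that row: a patient who is still rising has not fallen by more than 30%, so its hold condition applies.

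**Dose.** Let D be the dose when creatinine doubles and k the number of further halvings under the renal section.

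- Important Treatment Rules: D × 0.5 at every k.
- Worsening Renal Function: D × 0.5^(k+1).
- Ratio of the first to the second: 0.5 / 0.5^(k+1) = 2^k.

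The illustration takes D from the top doses of Figure 5a (ramipril 10 mg/d, enalapril 40 mg/d):

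| k | Time from doubling | Ramipril, Figure 5a rules / renal section | Enalapril, Figure 5a rules / renal section | Ratio |
|---|---|---|---|---|
| 0 | 0 h | 5 / 5 mg | 20 / 20 mg | 1 |
| 1 | 24–48 h | 5 / 2.5 mg | 20 / 10 mg | 2 |
| 2 | 72–96 h | 5 / 1.25 mg | 20 / 5 mg | 4 |

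The ratio does not depend on D, so it is the same for the other four listed drugs and for any starting dose.

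**Diuretics.** One text says the protocol does not determine diuretic treatment at any time. The other sets a minimum 50% reduction in renal injury. A protocol-set reduction and a statement that the protocol sets nothing cannot both hold for the same patient.

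**Precedence.** No section says which text governs.

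**The case against.** The strongest reply is that the bullets are a summary attached to a dosing chart, while Worsening Renal Function is the dedicated safety section, with a defined trigger, a recheck interval and separate branches. On that view the detailed text governs. Section 7 (Study Withdrawal) supports it: for acute kidney injury the medication concerned is to be adjusted or suspended. The early goal-directed section also limits doses to the maximum tolerated. So a reader might infer that the protocol obliges a physician to keep a dose that is too high, and the documents do not support that. What stands is that neither of these texts chooses between holding and halving again, and the Figure 5a bullet gives an explicit contrary order until a stated fall in creatinine.

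On diuretics, a reader might infer that the renal section also contradicts the Summary and General Procedure for Both Groups. That goes too far. Those are general statements. The renal section gives a reason for its cut (diuretics contribute to renal injury) and reads naturally as a specific exception. General Procedure itself ties treatment to clinical condition, and the control-group section already adjusts diuretic dose to renal function. Only the Figure 5a bullet, which excludes any protocol determination, truly clashes.

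It is also fair to say that the 4-fold gap is a corner case. Top doses are generally reached at about days 6 to 7 by patients titrated through the schedule (sooner by those admitted on maximal doses). The gap then needs 72 to 96 hours of continued rise, and algorithm dosing stops at discharge. That limits how often it can occur, but does not settle which dose is right when it does.

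**Conclusion.** The inconsistency is real and should be corrected. It is confined to two bullets of the Important Treatment Rules.

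1. **ACE-inhibitor/ARB.** For the patient still rising after the first halving, the Figure 5a dose is 2 times, then 4 times, the renal-section dose. In the other branches the rules agree.
2. **Diuretics.** No protocol-set change under the Figure 5a bullet, against a cut of at least 50% under the renal section.

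The size is stated per patient only. A reader might want a count: an assumed doubling rate of 2% to 10% would give 0.02 × 770 = 15.4 to 0.10 × 770 = 77 patients with renal injury. The documents give no such rate, nor the share whose creatinine keeps rising after the first halving, so no count is claimed.

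A reader might also infer that the diuretic rule would lower diuretic dose more in one arm and disturb the comparison. That would require renal injury to be more common in that arm, which the documents do not show. Randomization is stratified by site, so differences in site practice should be balanced between arms. Sample size, alpha and the primary analysis are unaffected. The Figures 4a / 4b references are a numbering slip and carry no weight here.

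**What to change.** Use the renal section's own rule in both places, so that no new threshold is introduced.

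- **Creatinine bullet, Important Treatment Rules.** Replace with: *Creatinine more than 100% above baseline: halve the ACE-inhibitor or ARB and re-measure at 24 to 48 hours. Still rising: halve again, every 48 hours, until it begins to fall. Unchanged, or less than 30% below peak: hold the current dose. At least 30% below peak: return to the schedule.*
- **Diuretic bullet, same list.** Add: *except the reduction in renal injury described under Worsening Renal Function.* Making the cut discretionary instead would also remove the clash, but would give up a safety instruction, so it is not proposed here.
- **Editorial only.** In Worsening Renal Function, change both references from Figures 4a / 4b to Figures 5a / 5b.

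The cost is amendment wording and an updated Figure 5a dosing sheet for sites. No added data, visits or patients are needed.
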